Appendix 3: Study Governance Considerations

Regulatory and Ethical Considerations

- This study will be conducted in accordance with the protocol and with the following:
 - Consensus ethical principles derived from international guidelines including the Declaration of Helsinki and Council for International Organizations of Medical Sciences (CIOMS) International Ethical Guidelines
 - Applicable ICH Good Clinical Practice (GCP) Guidelines
 - Applicable laws and regulations
- The protocol, protocol amendments, ICF, Investigator Brochure, and other relevant documents (eg, advertisements) must be submitted to an IRB/IEC by the investigator and reviewed and approved by the IRB/IEC before the study is initiated.
- Any amendments to the protocol will require IRB/IEC approval before implementation of changes made to the study design, except for changes necessary to eliminate an immediate hazard to study subjects.
- The investigator will be responsible for the following:
 - Providing written summaries of the status of the study to the IRB/IEC annually or more frequently in accordance with the requirements, policies, and procedures established by the IRB/IEC
 - Notifying the IRB/IEC of SAEs or other significant safety findings as required by IRB/IEC procedures
 - Providing oversight of the conduct of the study at the site and adherence to requirements of 21 CFR, ICH guidelines, the IRB/IEC, European regulation 536/2014 for clinical studies (if applicable), and all other applicable local regulations

Financial Disclosure

Investigators and sub-investigators will provide the sponsor with sufficient, accurate financial information as requested to allow the sponsor to submit complete and accurate financial certification or disclosure statements to the appropriate regulatory authorities. Investigators are responsible for providing information on financial interests during the course of the study and for 1 year after completion of the study.

Informed Consent Process

- The investigator or his/her representative will explain the nature of the study to the subject or his/her legally authorized representative and answer all questions regarding the study.
- Subjects must be informed that their participation is voluntary. Subjects will be required to sign a statement of informed consent that meets the requirements of 21 CFR 50, local regulations, ICH guidelines, Health Insurance Portability and Accountability Act (HIPAA) requirements, where applicable, and the IRB/IEC or study center.
- The medical record must include a statement that written informed consent was obtained before the subject was enrolled in the study and the date the written consent was obtained. The authorized person obtaining the informed consent must also sign the ICF.

- Subjects must be re-consented to the most current version of the ICF(s) during their participation in the study.
- A copy of the ICF(s) must be provided to the subject or the subject's legally authorized representative.

Data Protection

- Subjects will be assigned a unique identifier by the sponsor. Any subject records or datasets that are transferred to the sponsor will contain the identifier only; subject names or any information which would make the subject identifiable will not be transferred.
- The subject must be informed that his/her personal study-related data will be used by the sponsor in accordance with local data protection law. The level of disclosure must also be explained to the subject.
- The subject must be informed that his/her medical records may be examined by Clinical Quality Assurance auditors or other authorized personnel appointed by the sponsor, by appropriate IRB/IEC members, and by inspectors from regulatory authorities.

Publication Policy

- The results of this study may be published or presented at scientific meetings. If this is foreseen, the investigator agrees to submit all manuscripts or abstracts to the sponsor before submission. This allows the sponsor to protect proprietary information and to provide comments.
- The sponsor will comply with the requirements for publication of study results. In accordance with standard editorial and ethical practice, the sponsor will generally support publication of multicenter studies only in their entirety and not as individual site data. In this case, a coordinating investigator will be designated by mutual agreement.
- Authorship will be determined by mutual agreement and in line with International Committee of Medical Journal Editors authorship requirements.

Dissemination of Clinical Study Data

This study and its results will be posted on the US National Institutes of Health's website www.ClinTrials.gov.

Data Quality Assurance

- All subject data relating to the study will be recorded on printed or electronic CRF unless transmitted to the sponsor or designee electronically (eg, laboratory data). The investigator is responsible for verifying that data entries are accurate and correct by physically or electronically signing the CRF.
- The investigator must maintain accurate documentation (source data) that supports the information entered in the CRF.
- The investigator must permit study-related monitoring, audits, IRB/IEC review, and regulatory agency inspections and provide direct access to source data documents.
- The sponsor or designee is responsible for the data management of this study including quality checking of the data.

- Study monitors will perform ongoing source data verification to confirm that data entered into the CRF by authorized site personnel are accurate, complete, and verifiable from source documents; that the safety and rights of subjects are being protected; and that the study is being conducted in accordance with the currently approved protocol and any other study agreements, ICH GCP, and all applicable regulatory requirements.
- Records and documents, including signed ICFs, pertaining to the conduct of this study must be retained by the investigator for 2 years after study completion unless local regulations or institutional policies require a longer retention period (ie, at least 2-years after the last approval of a marketing application in an ICH region and until there are no pending or contemplated marketing applications in an ICH region or at least 2-years have elapsed since the formal discontinuation of clinical development of the investigational product). No records may be destroyed during the retention period without the written approval of the sponsor. No records may be transferred to another location or party without written notification to the sponsor.

Source Documents

- Source documents provide evidence for the existence of the subject and substantiate the integrity of the data collected. Source documents are filed at the investigator's site.
- Data reported on the CRF or entered in the eCRF that are transcribed from source documents must be consistent with the source documents or the discrepancies must be explained. The investigator may need to request previous medical records or transfer records, depending on the study. Also, current medical records must be available.

Study and Site Closure

The sponsor designee reserves the right to close the study site or terminate the study at any time for any reason at the sole discretion of the sponsor. Study sites will be closed upon study completion. A study site is considered closed when all required documents and study supplies have been collected and a study-site closure visit has been performed.

The investigator may initiate study-site closure at any time, provided there is reasonable cause and sufficient notice is given in advance of the intended termination.

Reasons for the early closure of a study site by the sponsor or investigator may include but are not limited to:

- Failure of the investigator to comply with the protocol, the requirements of the IRB/IEC or local health authorities, the sponsor's procedures, or GCP guidelines
- Inadequate recruitment of subjects by the investigator
- Discontinuation of further study treatment development

Appendix 4: Adverse Events: Definitions and Procedures for Recording, Evaluating, Follow-up, and Reporting

Definition of AE

AE Definition

• An AE is any untoward medical occurrence in a patient or clinical study subject, temporally associated with the use of study treatment, whether or not considered related to the study treatment.• A treatment-emergent adverse event (TEAE) is any AE that occurs or worsens in either intensity or frequency after exposure to study drug in the treatment phase.• NOTE: An AE can therefore be any unfavorable and unintended sign (including an abnormal laboratory finding), symptom, or disease (new or exacerbated) temporally associated with the use of study treatment.

Events Meeting the AE Definition


• Any abnormal laboratory test results (hematology, clinical chemistry, or urinalysis) or other safety assessments (eg, electrocardiogram, radiological scans, vital signs measurements), including those that worsen from baseline, considered clinically significant in the medical and scientific judgment of the investigator (ie, not related to progression of underlying disease).• Exacerbation of a chronic or intermittent pre-existing condition including either an increase in frequency and/or intensity of the condition.• New conditions detected or diagnosed after study treatment administration even though it may have been present before the start of the study.• Signs, symptoms, or the clinical sequelae of a suspected drug-drug interaction.• Signs, symptoms, or the clinical sequelae of a suspected overdose of either study treatment or a concomitant medication. Overdose per se will not be reported as an AE/SAE unless it is an intentional overdose taken with possible suicidal/self-harming intent. Such overdoses should be reported regardless of sequelae.• "Lack of efficacy" or "failure of expected pharmacological action" per se will not be reported as an AE or SAE. Such instances will be captured in the efficacy assessments. However, the signs, symptoms, and/or clinical sequelae resulting from lack of efficacy will be reported as AE or SAE if they fulfil the definition of an AE or SAE.
--

Events NOT Meeting the AE Definition

- Any clinically significant abnormal laboratory findings or other abnormal safety assessments which are associated with the underlying disease, unless judged by the investigator to be more severe than expected for the subject's condition.
- The disease/disorder being studied or expected progression, signs, or symptoms of the disease/disorder being studied, unless more severe than expected for the subject's condition.
- Medical or surgical procedure (eg, endoscopy, appendectomy): the condition that leads to the procedure is the AE.
- Situations in which an untoward medical occurrence did not occur (social and/or convenience admission to a hospital).
- Anticipated day-to-day fluctuations of pre-existing disease(s) or condition(s) present or detected at the start of the study that do not worsen.

Definition of SAE

If an event is not an AE per definition above, then it cannot be an SAE even if serious conditions are met (eg, hospitalization for signs/symptoms of the disease under study, death due to progression of disease).

A SAE is defined as any untoward medical occurrence that, at any dose:**a. Results in death****b. Is life-threatening**

The term 'life-threatening' in the definition of 'serious' refers to an event in which the subject was at risk of death at the time of the event. It does not refer to an event, which hypothetically might have caused death, if it were more severe.

c. Requires inpatient hospitalization or prolongation of existing hospitalization

In general, hospitalization signifies that the subject has been detained (usually involving at least an overnight stay) at the hospital or emergency ward for observation and/or treatment that would not have been appropriate in the physician's office or outpatient setting. Complications that occur during hospitalization are AEs. If a complication prolongs hospitalization or fulfills any other serious criteria, the event is serious. When in doubt as to whether "hospitalization" occurred or was necessary, the AE should be considered serious.

Hospitalization for elective treatment of a pre-existing condition that did not worsen from baseline is not considered an AE.

d. Results in persistent disability/incapacity

- The term disability means a substantial disruption of a person's ability to conduct normal life functions.

- This definition is not intended to include experiences of relatively minor medical significance such as uncomplicated headache, nausea, vomiting, diarrhea, influenza, and accidental trauma (eg, sprained ankle) which may interfere with or prevent everyday life functions but do not constitute a substantial disruption.

e. Is a congenital anomaly/birth defect

f. Other situations:

- Medical or scientific judgment should be exercised in deciding whether SAE reporting is appropriate in other situations such as important medical events that may not be immediately life-threatening or result in death or hospitalization but may jeopardize the subject or may require medical or surgical intervention to prevent one of the other outcomes listed in the above definition. These events should usually be considered serious.

Examples of such events include invasive or malignant cancers, intensive treatment in an emergency room or at home for allergic bronchospasm, blood dyscrasias or convulsions that do not result in hospitalization, or development of drug dependency or drug abuse.

Recording and AE and/or SAE

AE and SAE Recording

- When an AE/SAE occurs, it is the responsibility of the investigator to review all documentation (eg, hospital progress notes, laboratory reports, and diagnostics reports) related to the event.
- The investigator will then record all relevant AE/SAE information in the CRF (eg, event term, date and time of onset, date and time of resolution, anatomical site or system). If the AE/SAE is to an eye, the study eye or fellow eye must be identified.
- It is **not** acceptable for the investigator to send photocopies of the subject's medical records to Senju in lieu of completion of the AE/SAE CRF page.
- There may be instances when copies of medical records for certain cases are requested by Senju. In this case, all subject identifiers, with the exception of the subject number, will be redacted on the copies of the medical records before submission to Senju.
- The investigator will attempt to establish a diagnosis of the event based on signs, symptoms, and/or other clinical information. Whenever possible, the diagnosis (not the individual signs/symptoms) will be documented as the AE/SAE.

Assessment of Intensity

The investigator will make an assessment of intensity for each AE and SAE reported during the study and assign it to 1 of the following categories:

- Grade 1 (Mild): asymptomatic or mild symptoms; clinical or diagnostic observations only; intervention not indicated.

- Grade 2 (Moderate): minimal, local or non-invasive intervention indicated; limiting age appropriate instrumental ADL*.
- Grade 3 (Severe): medically significant but not immediately life-threatening; hospitalization or prolongation of hospitalization indicated; disabling; limiting self-care ADL.
- Grade 4 (Life threatening): urgent intervention indicated
- Grade 5 (Death): death related to AE

An event is defined as 'serious' when it meets at least 1 of the predefined outcomes as described in the definition of an SAE, NOT when it is rated as severe.

* Activities of daily living

Assessment of Causality

- The investigator is obligated to assess the relationship between study treatment and each occurrence of each AE/SAE.
- A "reasonable possibility" of a relationship conveys that there are facts, evidence, and/or arguments to suggest a causal relationship, rather than a relationship cannot be ruled out.
- The investigator will use clinical judgment to determine the relationship.
- Alternative causes, such as underlying disease(s), concomitant therapy, and other risk factors, as well as the temporal relationship of the event to study treatment administration will be considered and investigated.
- The investigator will also consult the Investigator's Brochure (IB) and/or Product Information, for marketed products, in his/her assessment.
- For each AE/SAE, the investigator **must** document in the medical notes that he/she has reviewed the AE/SAE and has provided an assessment of causality.
- There may be situations in which an SAE has occurred and the investigator has minimal information to include in the initial report to Senju. However, **it is very important that the investigator always make an assessment of causality for every event before the initial transmission of the SAE data to Senju.**
- The investigator may change his/her opinion of causality in light of follow-up information and send a SAE follow-up report with the updated causality assessment.
- The causality assessment is one of the criteria used when determining regulatory reporting requirements.

Follow-up of AEs and SAEs

- The investigator is obligated to perform or arrange for the conduct of supplemental measurements and/or evaluations as medically indicated or as requested by Senju to elucidate the nature and/or causality of the AE or SAE as fully as possible. This may include additional laboratory tests or investigations, histopathological examinations, or consultation with other health care professionals.
- Drug related AEs or SAEs will be followed up until resolution, stabilization, or the event is otherwise explained, or the subject is lost to follow-up.
- Non-drug-related AEs or SAEs will not be followed after the telephone follow-up call is complete. Any non-drug-related AEs or SAEs, that have not been resolved, stabilized, or otherwise explained by the follow-up telephone visit will be referred to the subjects Primary Care Physician for ongoing care.
- If a subject dies during participation in the study or during a recognized follow-up period, the investigator will provide Senju with a copy of any post-mortem findings including histopathology.
- New or updated information will be recorded in the originally completed CRF.
- The investigator will submit any updated SAE data to Senju within 24 hours of receipt of the information.

Reporting of SAEs**SAE Reporting to Senju via an Electronic Data Collection Tool**

- The primary mechanism for reporting an SAE to Senju will be the electronic data collection tool.
- If the electronic system is unavailable for more than 24 hours, then the site will use the paper SAE data collection tool (see next section).
- The site will enter the SAE data into the electronic system as soon as it becomes available.
- After the study is completed at a given site, the electronic data collection tool will be taken off-line to prevent the entry of new data or changes to existing data.
- If a site receives a report of a new SAE from a study subject or receives updated data on a previously reported SAE after the electronic data collection tool has been taken off-line, then the site can report this information on a paper SAE form (see next section) or to the Senju by telephone.
- Contacts for SAE reporting can be found in the Study Reference Manual.

SAE Reporting to Senju via Paper CRF

- Facsimile transmission of the SAE paper CRF is the preferred method to transmit this information to Senju.
- In rare circumstances and in the absence of facsimile equipment, notification by telephone is acceptable with a copy of the SAE data collection tool sent by overnight mail or courier service.
- Initial notification via telephone does not replace the need for the investigator to complete and sign the SAE CRF pages within the designated reporting time frames.
- Contacts for SAE reporting can be found in the Study Reference manual

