9.3.1. Time Period and Frequency for Collecting AE and SAE Information

All SAEs will be collected from the beginning of the run-in phase to the follow-up visit.

Medical occurrences that begin before the start of study treatment but after obtaining informed consent will be recorded on the Medical History/Current Medical Conditions section of the case report form (CRF) not the AE section.

All SAEs will be recorded and reported to the sponsor or designee within 24 hours, as indicated in [Appendix 4](#). The investigator will submit any updated SAE data to the sponsor within 24 hours of it being available.

Investigators are not obligated to actively seek AE or SAE in former study subjects. However, if the investigator learns of any SAE, including a death, at any time after a subject has been discharged from the study, and he/she considers the event to be reasonably related to the study treatment or study participation, the investigator must promptly notify the sponsor.

The method of recording, evaluating, and assessing causality of AE and SAE and the procedures for completing and transmitting SAE reports are provided in [Appendix 4](#).

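### The paper fallback for SAE reports is triggered only by an outage longer than the 24-hour reporting limit, so a site that waits for the trigger can report late

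*Combined protocol and SAP*

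**What the plan says.** Section 9.3.1 sets the deadline: "All SAEs will be recorded and reported to the sponsor or designee within 24 hours". The same sentence points to Appendix 4 for how this is done. It does not say from what moment the 24 hours run. Follow-up information has its own 24-hour limit, stated in Section 9.3.1 ("The investigator will submit any updated SAE data to the sponsor within 24 hours of it being available") and again in Appendix 4 ("The investigator will submit any updated SAE data to Senju within 24 hours of receipt of the information").

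Appendix 4, under Reporting of SAEs, gives the routes:

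- **Electronic.** "The primary mechanism for reporting an SAE to Senju will be the electronic data collection tool".
- **Paper, during an outage.** "If the electronic system is unavailable for more than 24 hours, then the site will use the paper SAE data collection tool". The data are then to be entered electronically when the system is back.
- **Telephone.** This comes under the paper route: "In rare circumstances and in the absence of facsimile equipment, notification by telephone is acceptable", with a copy of the form to follow by overnight mail or courier. The call "does not replace the need for the investigator to complete and sign the SAE CRF pages within the designated reporting time frames".
- **Paper or telephone with no waiting period.** This is allowed once the electronic tool has been taken off-line after the study is completed at a site.

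**The concern.** A backup route protects a deadline only if it can be used before the deadline passes. Here the outage must exceed 24 hours before the site is told to switch to paper, and the report itself is due within 24 hours. A site that finds the system down when it tries to report, and follows the outage instruction as written, has no time left when the instruction takes effect.

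What is at stake is timely safety reporting. Section 9.3.4 describes prompt notification of the sponsor as essential to its legal and ethical responsibilities, and the sponsor's own reports to regulators, ethics committees and investigators depend on it. The study escalates dose by cohort. Under Section 5.1 the next Part A cohort starts its run-in while the previous cohort's data are still being assessed.

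**Working it through.** The documents give no figure to reproduce, so the check is a timeline.

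**Inputs**

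- Reporting limit: 24 h (Section 9.3.1).
- Paper trigger: outage longer than 24 h (Appendix 4).
- Assumption: the clock starts at t = 0, when the site learns of the SAE.
- s = time at which the outage starts, in hours from t = 0 (negative if it started earlier). d = length of the outage in hours.
- The site has not reported before the outage starts, and it waits for either the paper trigger or the return of the system.

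**Formulas**

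- If d > 24, paper is triggered just after t = s + 24. Time left before the deadline = 24 − (s + 24) = −s.
- If d ≤ 24, paper is never triggered and electronic entry is possible again at t = s + d. Time left = 24 − (s + d).

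**Results**

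| Outage start s | Length d | Earliest report | Against the 24 h limit |
|---|---|---|---|
| 0 | > 24 h | after 0 + 24 = 24 h | late |
| 2 h | > 24 h | after 2 + 24 = 26 h | more than 2 h late |
| −10 h | > 24 h | after −10 + 24 = 14 h | up to 10 h left |
| 6 h | 20 h | 6 + 20 = 26 h | 2 h late |
| 0 | 20 h | 0 + 20 = 20 h | 4 h left |

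For outages over 24 hours, the time left is −s. It is zero or negative whenever the outage starts at or after awareness, and positive when it started earlier. For outages of 24 hours or less, the report is late when s + d exceeds 24.

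The same arithmetic applies to updated SAE data. There the start of the clock is stated, as availability of the data in Section 9.3.1 and receipt in Appendix 4.

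**Does another provision close the gap?**

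- Telephone is a substitute for fax within the paper route and is limited to rare circumstances. The signed form stays due within the reporting time frame, so a call alone does not meet the requirement.
- The permission without a waiting period covers the time after study completion at the site, not an outage during the study.
- The opening list of Section 9 asks for immediate safety concerns to be discussed with the sponsor at once, to decide whether a subject continues. That is not the SAE report required by Section 9.3.1.

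**The case against.** The strongest reply is that Appendix 4 makes paper compulsory after 24 hours of outage and does not bar it sooner. The deadline in Section 9.3.1 is unconditional, and Appendix 4 itself ties the SAE pages to the reporting time frames. A site that faxes the form before hour 24 satisfies both. This stands. A reader might infer that paper is forbidden until the trigger, or that the two rules cannot both be met in an outage. The text supports neither. What remains is that no earlier route is stated, and a site has to act ahead of the one trigger it is given.

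A reader might also infer that every long outage makes the report late. It does not: an outage already under way when the site learns of the SAE can leave time, and many shorter ones end early enough for electronic entry.

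Three further points limit the consequence:

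- The sponsor need not be uninformed. Section 9 asks for immediate discussion of urgent concerns, and the cohort reviews in Section 5.1 are made by the investigator and the sponsor on the assembled data at a single center. A form delayed by hours would not by itself bypass those reviews.
- It is tempting to add weight by calling this a first-in-human study. The Synopsis and Section 3.1 say only that it is the first study in humans to evaluate effectiveness or efficacy in dry eye disease. The contents list a section on clinical studies whose text is not available here.
- Appendix 4 refers to the Study Reference Manual for SAE reporting contacts. Whether the manual covers outages cannot be checked.

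**Conclusion.** The concern holds in a limited form. The only outage instruction for the study period has a trigger longer than the deadline it should protect. A site that has not yet reported and waits for it is late in every outage of more than 24 hours that begins at or after awareness. It is also late in a shorter outage if the system returns after hour 24.

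This rests on two assumptions: that the clock for the initial report starts when the site learns of the event, and that the site treats the trigger as the point at which to switch. The documents say nothing on how often or how long the system is down, so the number of reports affected cannot be estimated and may be small. The consequence is late safety reporting to the sponsor and, through it, to regulators. Sample size, endpoints and analyses are untouched.

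**What to change.** Reconcile Section 9.3.1 with Appendix 4. In the outage sentence of Appendix 4, replace the condition of more than 24 hours' unavailability with the condition that the system is unavailable when an SAE is to be reported. The existing paper form by fax, or telephone followed by the form, would then be used within the 24-hour limit. Electronic entry once the system returns is already required and can stay. In the same edit, Section 9.3.1 could state when the 24 hours start for an initial report.

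The cost is one sentence in the protocol, a matching check of the Study Reference Manual, and an occasional duplicate form when a short outage ends soon after the paper report is sent. The paper form and fax route already exist.
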